12.5.5 Exploratory (efficacy) analysis

The exploratory efficacy endpoints assessing change-from-baseline BP will be analysed using mixed models for repeated measured (MMRM). The models will include treatment subgroup, analysis visit, treatment subgroup-by-visit interaction, the baseline BP value as a covariate, and patient as a random effect. An unstructured covariance structure was used to model the within-patient errors. The exploratory efficacy endpoint for proportion of patients achieving controlled BP will be analysed using a logistic MMRM with similar terms.

Additional details will be summarized in the Statistical Analysis Plan.

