### 7.4.1 Mean Change (Endpoints 3.1 and 3.2)

**Endpoint 3.1**: Change in mean sitting SBP and DBP between Visit 1 (Week -4) and Visit 2 (Week 0), Visit 3 (Week 4) and Visit 4 (Week 8).

**Endpoint 3.2**: Change in mean sitting SBP and DBP for uncontrolled patients at Visit 3 (Week 4), between Visit 2 (Week 0) and Visit 3 (Week 4).

Endpoints 3.1 and 3.2 will be analyzed using mixed models for repeated measured (MMRM) to assess the mean change in SBP and DBP. The models will be built as follows:

- Endpoint 3.1
  - *Response* = change from screening BP
  - *Covariates* = treatment subgroup, study visit, treatment subgroup-by-visit interaction, screening BP values
  - *Random effect* = patient
  - Covariance matrix = unstructured
    - In the event of lack of model convergence, other covariance structures may be used.
    - If all MMRM fail to converge, this endpoint will be analyzed as described in section 7.4.1.1 below.
- Endpoint 3.2
  - *Response* = change from baseline BP

- *Covariates* = treatment subgroup, study visit, treatment subgroup-by-visit interaction, baseline BP values
- *Random effect* = patient
- *Covariance matrix* = unstructured
  - In the event of lack of model convergence, other covariance structures may be used.
  - If all MMRM fail to converge, this endpoint will be analyzed as described in section 7.4.1.1 below.

Least-squares (LS) means, standard error (SE), and 95% CIs for mean change from screening/baseline for BP will be presented by visit and treatment subgroup. The LS-means difference, SE, 95% CI, and two-sided p-value for the difference between treatment subgroups in mean change from screening/baseline for sitting SBP and DBP will be presented where a p-value of  $\leq$  0.05 indicates a significant difference between groups.

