#### 7.4.1.1 Model Nonconvergence

If the above MMRMs fail to converge, endpoints 3.1 and 3.2 will be analyzed using independent sample t-tests to compare the mean change in BP in the test group to the comparison group (test/comparison groups defined in section 7.4).

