## Table 14.2.4.1 Difference in Mean Change for Sitting Systolic (SBP) and Diastolic Blood Pressure (DBP) From Visit 1 to Visits 2, 3, and 4 (Full Analysis Set and Efficacy Population)

				SBP		DBP		
			-	ZOF/AML [4]	ACE-i/CCB [5]	ZOF/AML [4]	ACE-i/CCB [5]	
Therapy Type	Visit [1]	Statistic Type [2,3]	Statistic	(N=xx)	(N=xx)	(N=xx)	(N=xx)	
Monotherapy	Visit 2 CFS	MMRM	n	ХХ	XX	XX	ХХ	
			LSM (SE)	xx.x (xx.xxx)	xx.x (xx.xxx)	xx.x (xx.xxx)	xx.x (xx.xxx)	
			95% CI	(xx.x, xx.x)	(xx.x, xx.x)	(xx.x, xx.x)	(xx.x, xx.x)	
		v. ACE-i/CCB	LSM Difference (SE)	xx		xx		
			95% CI	xx.x (xx.xxx)		xx.x (xx.xxx)		
			p-value	x.xxx		x.xxx		
Combined Therapy	Visit 3 CFB	MMRM	n	xx	xx	xx	xx	
			LSM (SE)	xx.x (xx.xxx)	xx.x (xx.xxx)	xx.x (xx.xxx)	xx.x (xx.xxx)	
			95% CI	(xx.x, xx.x)	(xx.x, xx.x)	(xx.x, xx.x)	(xx.x, xx.x)	
		v. ACE-i/CCB	LSM Difference (SE)	xx		xx		
			95% CI	xx.x (xx.xxx)		xx.x (xx.xxx)		
			p-value	x.xxx		x.xxx		
	Visit 4 CFB	MMRM	n	xx	xx	xx	xx	
			LSM (SE)	xx.x (xx.xxx)	xx.x (xx.xxx)	xx.x (xx.xxx)	xx.x (xx.xxx)	
			95% CI	(xx.x, xx.x)	(xx.x, xx.x)	(xx.x, xx.x)	(xx.x, xx.x)	
		v. ACE-i/CCB	LSM Difference (SE)	xx		xx		
			95% CI	xx.x (xx.xxx)		xx.x (xx.xxx)		
			p-value	x.xxx		x.xxx		

Note: The Monotherapy analysis (Visit 2) is performed on the Full Analysis Set. The Combined Therapy analysis (Visits 3 and 4) are performed on the Efficacy Population. [1] CFS = Change from Screening (Visit 1). CFB = Change from Baseline (Visit 2).

[2] MMRM = Mixed Model Repeated Measures.

[3] A separate model is used for the monotherapy and combined therapy analyses. The models use an unstructured covariance matrix; change from screening (monotherapy) or baseline (combined therapy) for SBP/DBP as the response variable; visit, treatment subgroup, visit\*treatment subgroup interaction, and screening (monotherapy) or baseline (combined therapy) SBP/DBP as covariates; and a random effect for patient.

[4] ZOF/AML subgroup: Patients who were on ZOF 30 mg or AML 5 mg at Visit 1 (Week -4) and continued on same therapies.

[5] ACE-i/CCB subgroup: Patients who switched to ZOF 30 mg or AML 5 mg from any other ACE-i or CCBs at Visit 1 (Week -4).

Source: Listing 16.2.6

Program Name: XXXX.SAS

Programming Note:

• If a different covariance structure is used in case of model nonconvergence, footnote 3 should be updated accordingly.

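### The Endpoint 3.1 and 3.2 mixed models contain terms the data cannot identify, and the non-convergence fallback drops the baseline adjustment

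*SAP*

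**What the plan says.** Endpoint 3.2 is the change in SBP and DBP from Visit 2 to Visit 3 in patients still uncontrolled at Visit 3. SAP 7.4.1 gives it an MMRM with covariates "treatment subgroup, study visit, treatment subgroup-by-visit interaction, baseline BP values", patient as a random effect and an unstructured covariance matrix. Shell Table 14.2.4.2 repeats those terms but has one result row, the Visit 3 change.

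Endpoint 3.1 is the change from screening at Visits 2, 3 and 4. Its covariates are "treatment subgroup, study visit, treatment subgroup-by-visit interaction, screening BP values", again with a random patient effect and an unstructured matrix. Shell Table 14.2.4.1 splits it: "A separate model is used for the monotherapy and combined therapy analyses". The first model then holds Visit 2 only and the second holds Visits 3 and 4. (The shell also takes the Visit 3 and 4 changes from Visit 2 and not from screening. That is a separate inconsistency.)

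Protocol 12.5.5 says where the unstructured matrix sits: "patient as a random effect. An unstructured covariance structure was used to model the within-patient errors".

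If a model does not converge, SAP 7.4.1 says: "In the event of lack of model convergence, other covariance structures may be used". If all of them fail, SAP 7.4.1.1 says "endpoints 3.1 and 3.2 will be analyzed using independent sample t-tests". No blood pressure covariate is named for those tests.

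**The concern.** An MMRM needs repeated measurements to separate visit effects and within-patient covariance. Endpoint 3.2 and the Visit 2-only model have none. For Endpoint 3.1 an unstructured matrix already has a free parameter for every variance and covariance, which leaves nothing for a random patient effect to estimate.

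What is at stake is prespecification. The planned comparison of continued with switched patients is adjusted for baseline or screening BP. As written, whether the reported comparison stays adjusted can depend on how software treats a non-identifiable model and on an unordered choice of other structures. The SAP attaches a significance statement at p ≤ 0.05 to the result, and the two subgroups are not randomised.

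**Working it through.** The plan states no sample size, power or expected difference for Endpoints 3.1 and 3.2, so there is no figure to reproduce. The only documented number used is the 10 mmHg SD of the DBP change (Protocol 12.2, SAP 4.6).

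**1. Fixed effects, one visit.** The columns are intercept, subgroup, visit, subgroup-by-visit and baseline BP, five in all. Visit is constant and equals the intercept; the interaction equals subgroup. The rank is 3: intercept, subgroup and baseline BP, which is an ANCOVA.

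**2. Covariance parameters.** With k visits the marginal covariance is V = τ²J + R, where τ² is the patient variance, J is a matrix of ones and R is the residual matrix. V has k(k+1)/2 distinct elements, and an unstructured R uses all of them. Adding τ² gives one too many.

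| Analysis | Visits | Parameters | Identifiable |
|---|---|---|---|
| Endpoint 3.2 | 1 | 1 + 1 = 2 | 1 |
| Shell 14.2.4.1, monotherapy | 1 | 1 + 1 = 2 | 1 |
| Shell 14.2.4.1, combined therapy | 2 | 3 + 1 = 4 | 3 |
| Endpoint 3.1 as in SAP 7.4.1 | 3 | 6 + 1 = 7 | 6 |

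**3. Does changing the structure help?** With one visit it does not while the random effect stays: independent residuals give 2 parameters and compound symmetry gives 3, with 1 identifiable in each case. With two or three visits, a random patient effect plus independent residuals has 2 parameters, both identifiable, and keeps the BP covariate.

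**4. Does the subgroup difference survive?** Yes. For Endpoint 3.1 the fixed effects have full rank: 2 subgroups × 3 visits + 1 covariate = 7. In one simulated data set (216 patients, three visits, invented covariance, equal subgroups), fixing τ² at 0, 10, 20 and 30 gave the same REML log-likelihood (-1653.4873), Visit 2 subgroup difference (1.819) and standard error (1.114). Only the split of variance is undetermined. For one record per patient, fits to simulated data in a package other than the planned SAS reported convergence and returned the ANCOVA point estimate, but the reported standard error did not always match ANCOVA's. SAS behaviour was not tested.

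**5. Precision lost in the fallback.** Take between-patient SD b and visit-to-visit SD w. Then Var(change) = 2w², Var(baseline) = b² + w² and Cov(change, baseline) = -w². The share of variance removed by adjustment is w²/[2(b² + w²)]. Assume b = 8, so b² = 64:

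| w | SD of change, w√2 | Share removed |
|---|---|---|
| 4 | 5.7 | 16/160 = 10% |
| 5.5 | 7.8 | 30.25/188.5 = 16% |
| 7.07 | 10 | 50/228 = 22% |

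Only the last row matches the documented SD of change. Working instead from an assumed baseline to follow-up correlation r with equal SDs, the variance ratio of ANCOVA to t-test is (1 + r)/2. For r = 0.3, 0.5 and 0.7 the t-test standard error is 1.24, 1.15 and 1.08 times that of ANCOVA. The gain is somewhat smaller if the subgroups differ in mean baseline BP.

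**6. After the change.** ANCOVA for one-record analyses has rank 3 with 3 columns. Endpoint 3.1 without the random effect has 6 covariance parameters, all identifiable.

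**The case against.** The strongest reply is that these are matters of specification tidiness. The quantity to be reported, the subgroup difference in mean change, is identified in every model; software may drop aliased columns or set a variance to zero and report it. Where that happens, Endpoint 3.2 already gives the ANCOVA estimate. This stands, and it limits the point.

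A reader might infer that the plan must end in t-tests. The documents do not support that. An unidentifiable variance split is not the same as non-convergence, other structures may be tried first, and the t-test applies only if all models fail. For Endpoint 3.1 an identifiable structure that keeps the covariate exists (step 3). For the one-record analyses no structure cures the fault while the random effect remains, so the risk is real there but still not certain.

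A reader might also infer that the t-test would create a spurious subgroup difference. That is not established. With a baseline gap, the two estimates differ by (1 - r) per 1 mmHg, or 0.7, 0.5 and 0.3 mmHg for r = 0.3, 0.5 and 0.7. Which one is biased depends on whether the gap is stable or regresses to a common mean, and the documents do not say. In non-randomised groups the two analyses answer different questions. What stands is that the fallback changes the question without saying so.

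Finally, SAP 7.4.1 read alone could mean the usual repeated-measures matrix, with patient named only as the subject. Endpoint 3.1 would then be identifiable. Protocol 12.5.5 and the shell footnotes point the other way, since they list both components.

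**Conclusion.** The specification is wrong as written for Endpoint 3.2 and the Visit 2-only model, and over-parameterised by one covariance parameter for Endpoint 3.1 and its Visits 3 and 4 version. This follows from the model statements alone and needs no assumed values. Non-convergence is possible, not demonstrated.

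If the fallback is reached, the comparison moves from baseline-adjusted to unadjusted and loses precision. The 22% figure rests on an assumed between-patient SD of 8 mmHg, a simple two-component variance model, and an SD of change that the documents give for DBP from Visit 2 to Visit 4. It is borrowed here for other intervals and, in Endpoint 3.2, for a selected subset. No SD is documented for SBP. The endpoints are exploratory, and no primary or secondary conclusion depends on them. The correction is worth making because it costs little and fixes the analysis in advance.

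**What to change.** - **Endpoint 3.2 and the Visit 2-only model:** specify ANCOVA of change on subgroup and baseline BP (screening BP for Visit 2). Remove visit, the interaction, the random effect and the covariance statement.
- **Endpoint 3.1 and the Visits 3 and 4 model:** keep the unstructured residual covariance, delete the random patient effect, and list the alternative structures in the order they will be tried.
- **SAP 7.4.1.1:** make the fallback an ANCOVA at each visit in place of the independent-sample t-test.

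The edits fall in SAP 7.4.1 and 7.4.1.1 and the footnotes to shell Tables 14.2.4.1 and 14.2.4.2, with a line in SAP 10.2 recording the departure from Protocol 12.5.5. Protocol section 12 lets the SAP modify planned analyses and ties an amendment to major changes in the primary endpoint or its analysis, so none appears to be needed. The data are already collected. The cost is wording and simpler programs. ANCOVA keeps the comparison the plan already intends; it does not remove confounding between non-randomised subgroups.

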#### 7.4.1.1 Model Nonconvergence

If the above MMRMs fail to converge, endpoints 3.1 and 3.2 will be analyzed using independent sample t-tests to compare the mean change in BP in the test group to the comparison group (test/comparison groups defined in section 7.4).

### 7.4.2 Proportion of Patients (Endpoints 3.3 and 3.4)

**Endpoint 3.3**: Monotherapy: number and proportion of patients achieving the BP goal (sitting BP  $\leq 130/80$  mmHg) at Visit 2 (Week 0). Combination therapy: number and proportion of patients achieving the BP goal (sitting BP  $\leq 130/80$  mmHg) at Visit 3 (Week 4).

**Endpoint 3.4**: Monotherapy: number and proportion of patients divided in subgroup by the hypertension grade, the presence of diabetes and/or of hypercholesterolemia achieving the BP goal (sitting BP  $\leq$ 130/80 mmHg) at Visit 2 (Week 0). Combination therapy: number and proportion of patients divided in subgroup by the hypertension grade, the presence of diabetes and/or of hypercholesterolemia achieving the BP goal (sitting BP  $\leq$ 130/80 mmHg) at Visit 3 (Week 4) and Visit 4 (Week 8).

Endpoints 3.3 and 3.4 will be analyzed using a logistic MMRM to assess the proportion of patients achieving the BP goal (sitting BP  $\leq$ 130/80 mmHg). The models will be built as follows:

- Endpoint 3.3
  - *Response* = achieving BP goal (sitting BP ≤130/80 mmHg)
  - *Covariates* = treatment subgroup, study visit, treatment subgroup-by-visit interaction, baseline BP values
  - *Random effect* = patient
  - Covariance matrix = unstructured
    - In the event of lack of model convergence, other covariance structures may be used.
    - If all logistic MMRM fail to converge, this endpoint will be analyzed as described in section 7.4.2.1 below.

- Endpoint 3.4 by hypertension grade
  - *Response* = achieving BP goal (sitting BP ≤130/80 mmHg)
  - *Covariates* = treatment subgroup, study visit, treatment subgroup-by-visit interaction, baseline BP values
  - *Random effect* = patient
  - Covariance matrix = unstructured
    - In the event of lack of model convergence, other covariance structures may be used.
    - If all logistic MMRM fail to converge, this endpoint will be analyzed as described in section 7.4.2.1 below.
  - Stratification factor = Baseline hypertension grade
- Endpoint 3.4 by presence of diabetes and/or of hypercholesterolemia
  - *Response* = achieving BP goal (sitting BP ≤130/80 mmHg)
  - *Covariates* = treatment subgroup, study visit, treatment subgroup-by-visit interaction, baseline BP values
  - *Random effect* = patient
  - *Covariance matrix* = unstructured
    - In the event of lack of model convergence, other covariance structures may be used.
    - If all logistic MMRM fail to converge, this endpoint will be analyzed as described in section 7.4.2.1 below.
  - *Stratification factor =* presence of diabetes and/or of hypercholesterolemia at baseline

The number (n), proportion (%), and 95% CI of the proportion of patients achieving controlled BP will be presented by visit and treatment subgroup. The odds ratio (OR), 95% CI of the OR, and two-sided p-value for the difference between treatment subgroups in proportion of patients achieving controlled BP will be presented where a p-value of  $\leq$  0.05 indicates a significant difference between groups.

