### 5.2 Study Variables

### 5.2.1 Baseline

Patients are instructed to take the study treatment after all visit evaluations have been performed on scheduled visit days. Assessments performed at Visit 2 will be considered Baseline since the first dose combination therapy (ZOF/AML) occurs after the completion of Visit 2 assessments. For assessments performed at Visit 1 and not Visit 2 (e.g., laboratory and ECG assessments), the Visit 1 assessment will be considered Baseline.

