### 7.1 Efficacy Variable Derivations

### 7.1.1 Blood Pressure (BP) Goal (Controlled v Uncontrolled)

Multiple endpoints (2.3, 3.3, and 3.4) involve patients meeting the BP goal of sitting  $BP \le 130/80$  mmHg at Visit 2 (Week 0), Visit 3 (Week 4) and Visit 4 (Week 8).

A patient will be considered to have met the BP goal (controlled BP) if their SBP  $\leq$  130 mmHg AND their DBP  $\leq$  80 mmHg. If a patient meets one of these criteria but not the other, then they will not be considered to have met the BP goal. That is, a patient's BP is considered uncontrolled if their SBP > 130 mmHg OR their DBP > 80 mmHg.

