[2] A separate model is used for the monotherapy and combined therapy analyses. Models use an unstructured covariance matrix; achieving sitting BP goal as the response variable; visit, treatment subgroup, visit\*treatment subgroup interaction, and screening (monotherapy) or baseline (combined therapy) SBP/DBP as covariates; and a random effect for patient.

[3] A patient is considered to have met the Blood Pressure (BP) goal (controlled BP) if their SBP  $\leq$  130 mmHg AND their DBP  $\leq$  80 mmHg.

[4] n = number of patients who have achieved sitting BP goal at that visit. N = number of patients with data at that visit, regardless of BP goal status.

[5] ZOF/AML subgroup: Patients who were on ZOF 30 mg or AML 5 mg at Visit 1 (Week -4) and continued on same therapies.

[6] ACE-i/CCB subgroup: Patients who switched to ZOF 30 mg or AML 5 mg from any other ACE-I or CCBs at Visit 1 (Week -4).

Source: Listing 16.2.6

Program Name: XXXX.SAS

Programming Note:

• If a different covariance structure is used in case of model nonconvergence, footnote 2 should be updated accordingly.

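### SAP 7.4.2 adjusts the Visit 2 BP-goal comparison for Visit 2 BP itself, which heavily biases the subgroup odds ratio towards 1; the table shells use screening BP, and the SAP does not say which prevails

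*SAP*

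**What the plan says.** - **Baseline.** SAP 5.2.1: "Assessments performed at Visit 2 will be considered Baseline". BP is measured at Visit 2, so baseline BP is Visit 2 BP.
- **Outcome.** SAP 7.1.1 derives the goal from the readings of the visit concerned: "a patient's BP is considered uncontrolled if their SBP > 130 mmHg", or if DBP exceeds 80 mmHg.
- **Model.** SAP 7.4.2: "Endpoints 3.3 and 3.4 will be analyzed using a logistic MMRM to assess the proportion of patients achieving the BP goal". The monotherapy time point for both endpoints is Visit 2. All three specifications (3.3, 3.4 by hypertension grade, 3.4 by diabetes and/or hypercholesterolemia) list "treatment subgroup, study visit, treatment subgroup-by-visit interaction, baseline BP values", plus a random patient effect.
- **Reported result.** An odds ratio, its 95% CI and a "two-sided p-value for the difference between treatment subgroups in proportion of patients achieving controlled BP will be presented". The subgroups are patients who stayed on ZOF 30 mg or AML 5 mg and patients switched to them from another ACE inhibitor or CCB (SAP 7.4).
- **Shells.** Footnote 2 of Table 14.2.4.3 reads "A separate model is used for the monotherapy and combined therapy analyses" and lists "screening (monotherapy) or baseline (combined therapy) SBP/DBP as covariates; and a random effect for patient". Tables 14.2.4.4.1 and 14.2.4.4.2 carry the same specification.
- **Elsewhere.** SAP 7.4.1 uses screening BP for Endpoint 3.1. Protocol 12.5.5 names baseline BP as covariate and asks for a logistic model with similar terms.

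**The concern.** At Visit 2 the response is computed from the same two readings that enter the model as covariates. Once Visit 2 SBP and DBP are known, subgroup adds nothing about whether the goal was met, so the subgroup coefficient no longer measures the difference in control rates. SAP 7.4.2 would nevertheless read its p-value as evidence on whether the groups differ. At stake is a misleading finding of no difference between continued and switched patients after the run-in. The text and the shells also lead two analysts to different models for the same table cell.

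**Working it through.** The plan states no power or effect size for these endpoints, so there is no figure of its own to reproduce.

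**Step 1: logic.** Let S2 and D2 be Visit 2 SBP and DBP, G the subgroup, and Y2 = 1 if S2 ≤ 130 and D2 ≤ 80, otherwise 0. Then P(Y2 = 1 | S2, D2, G) is 0 or 1 and does not depend on G. With screening values S1 and D1, P(Y2 = 1 | S1, D1, G) can depend on G, and that is the comparison intended.

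**Step 2: Visit 2-only logistic regression.** 400 simulated trials per scenario, with 290 patients (the planned number screened, SAP 4.1), two equal subgroups, and two-sided alpha 0.05 (SAP 5.5).

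Assumed, because the documents give no values:
- Visit 1 mean 150/94 (SD 8/6).
- Visit 2 mean 135/84 or 138/86 (SD 12/8).
- SBP–DBP correlation 0.5 and Visit 1–Visit 2 correlation 0.5.
- Subgroup shift in Visit 2 DBP of 0, 3 or 5 mmHg, with an SBP shift 1.5 times as large.

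| Visit 2 mean | DBP shift | Control rates | Crude OR | Screening BP: median OR, rejection | Visit 2 BP: median OR, rejection |
|---|---|---|---|---|---|
| 135/84 | 0 | 17.5% v 17.5% | 1.00 | 0.99, 6% | 0.97, 4% |
| 135/84 | 3 | 29.9% v 17.4% | 2.02 | 2.32, 76% | 0.97, 4% |
| 135/84 | 5 | 40.5% v 17.6% | 3.19 | 3.89, 100% | 1.01, 4% |
| 138/86 | 0 | 11.2% v 11.0% | 1.02 | 1.02, 4% | 1.05, 5% |
| 138/86 | 3 | 21.2% v 11.1% | 2.15 | 2.43, 69% | 1.03, 5% |
| 138/86 | 5 | 30.0% v 11.4% | 3.32 | 3.98, 99% | 1.04, 7% |

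For the second row, the crude odds ratio is (0.299/0.701)/(0.174/0.826) = 2.02. Its standard error is 0.56 with Visit 2 BP against 0.31 with screening BP, a ratio of 1.8. Every fit returned an estimate.

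**Step 3: a model closer to the SAP text.** SAP 7.4.2 lists one model per endpoint with visit and interaction terms. Pooled versions (Visits 2 and 3, common slopes for baseline BP, no random effect) were simulated under three sets of assumed values:
- True crude OR 2.13: Visit 2 OR 1.17, rejection 4% (10% with clustered errors). True crude OR 3.27: OR 1.34, rejection 6–13%.
- The BP values of Step 2, an assumed add-on effect of 8/5 mmHg, Visit 3 only for patients uncontrolled at Visit 2, clustered errors, 120 runs. 3 mmHg shift: OR 1.28–1.32, rejection 9–13%. 5 mmHg shift: OR 1.49–1.55, rejection 25–29%.
- True crude ORs of 2.1 and 3.3: OR 1.2 in both, rejection 4–7%.

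Pooling leaves some of the difference visible because one common slope must also fit Visit 3, where Visit 2 BP does not determine the outcome. The slope is then too shallow at Visit 2 to absorb the whole subgroup effect.

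**The case against.** **The right covariate is already in the package.** SAP section 11 refers to the shells, and all three affected shells specify screening BP in a separate monotherapy model. That is true, and it supplies most of the fix. It does not settle the matter. The SAP (23 May 2022) is dated after the shells (16 May 2022), its history records a clarification of endpoints and analysis methods, and the old covariate remains in all three specifications. Section 11 exempts only minor layout and formatting changes to the outputs from a SAP modification. Section 10 does not mention the difference.

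**The difference is not wholly removed.** A reader might infer that the SAP text erases any subgroup difference and drives the odds ratio to 1 whatever the truth. The documents do not support that. It describes a Visit 2-only model with Visit 2 BP, which combines the shells' split by period with the SAP text's covariate and appears in neither. The pooled model attenuates heavily but incompletely. This objection stands.

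**The scope is narrow.** This also stands. Endpoints 3.3 and 3.4 are exploratory and are defined as numbers and proportions. Those proportions and their CIs do not depend on the model, so a real contrast would still show in the same table.

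**Non-convergence has a fallback.** SAP 7.4.2.1 then gives binomial intervals and an odds ratio by visit. Because the goal requires two conditions at once, a model linear in SBP and DBP is generally not perfectly separated, and no 290-patient fit failed. In small strata the Visit 2-only model did fail often (15% of runs at n = 80 and 69% at n = 40, control 21% v 11%). The fallback is therefore a partial backstop for Endpoint 3.4 only.

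**Conclusion.** The specification in SAP 7.4.2 is wrong as written for the Visit 2 part of Endpoints 3.3 and 3.4, and it conflicts with the shells. Followed literally, it gives a Visit 2 odds ratio, CI and p-value heavily biased towards no difference. True crude odds ratios of about 2.0–3.3 become about 1.0 (Visit 2-only) or about 1.2–1.5 (pooled), with rejection of roughly 4–29%, against odds ratios of 2.3–4.0 and rejection of 69–100% with screening BP.

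The direction follows from the definitions alone. The sizes rest on assumed BP means, SDs, correlations and shifts, and on models without the random patient effect, which cannot be identified from a single monotherapy outcome visit.

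A reader might extend the problem to the reported control rates, to Visits 3 and 4, or to the main conclusions. None of that follows. The proportions and their CIs are observed values, Visit 2 BP precedes combination therapy and is a proper covariate for Visits 3 and 4, and no primary or secondary analysis uses these models.

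**What to change.** In SAP 7.4.2, for Endpoint 3.3 and both Endpoint 3.4 models:

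1. Fit a separate Visit 2 (monotherapy) logistic regression of the BP goal on treatment subgroup and screening (Visit 1) SBP and DBP, as the shells already have it. SAP section 7 puts the Visit 2 goal on the FAS and other efficacy analyses on the EFF population, which also calls for separate models.
2. Use Visit 2 SBP and DBP as covariates only in the combined-therapy models for Visits 3 and 4.
3. Remove the visit, subgroup-by-visit and random-patient terms from the Visit 2 model in both the SAP text and the footnotes of Tables 14.2.4.3, 14.2.4.4.1 and 14.2.4.4.2, since there is only one monotherapy outcome visit.

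The cost is wording in the SAP and three shell footnotes, to be settled before database lock. It needs no new data and does not affect the sample size.
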